10.4 Patient Baseline Characteristics

Patient baseline characteristics, including age, predisposition to hypersensitivity, and concurrent illness, will be tabulated.

10.5 Treatment Given

The treatment status of Leuplin PRO and treatment status of prostate cancer drug other than Leuplin PRO will be tabulated.

10.6 Matters on Safety

For patients included in safety evaluation, data will be tabulated as described below. AEs will be coded according to the MedDRA/J and summarized using preferred term (PT) and system organ class (SOC).

10.6.1 Occurrence of Adverse Events

For AEs reported during the observation period, the incidence will be tabulated by type, time of onset, seriousness, and causal relationship to Leuplin PRO. In addition, events listed as the safety specifications for the surveillance in “2. Summary of Pharmacovigilance Plan” in the risk management plan will be tabulated separately.

10.6.2 Factors that May Affect the Safety

For ADRs reported during the observation period, the incidence will be tabulated by patient background factors (e.g., disease status, presence or absence of concurrent renal impairment, presence or absence of concurrent hepatic impairment) and treatment status of Leuplin PRO.

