3.2 Rationale

To evaluate potential effects of differences between Leuplin PRO and Leuplin SR, that is, difference amounts of leuprorelin acetate administered in a single dose and different time profiles of serum drug concentration after administration, on the safety, it was decided to investigate the occurrence of injection site reaction and other adverse drug reactions (ADRs) with an incidence of 1% or higher, including the time of onset, incidence, and seriousness.

The sample size of 300 patients was determined to detect ADRs with an incidence of 1% or higher at a probability of 95% or higher.

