1.1 List of Terms and Abbreviations

- Leuplin PRO: Leuplin PRO for Injection Kit 22.5 mg is abbreviated as Leuplin PRO.
- Adverse drug reaction (ADR), etc.: ADR, etc. is an abbreviation of ADR/infection. ADRs, etc. refer to all adverse events (AEs) other than those assessed by the investigator to be not related to Leuplin PRO. In this document, “adverse drug reactions/infections” is used in titles, and “ADRs, etc.” is used in the text and tables.
- Serious adverse event (SAE): A SAE is an adverse event assessed by the investigator to be serious. Events included in the MedDRA code list in Takeda Medically Significant AE List will be handled as serious even if assessed by the investigator to be not serious.
- Causal relationship: An event assessed as not related to Leuplin PRO will be handled as “not related.” Events not unrelated to Leuplin PRO in the text and tables refer to all events other than those assessed as not related to Leuplin PRO.
- Summary statistics: Collective term for number of patients, mean, standard deviation, maximum, minimum, and quartiles
- Patient with no CRF collected: Enrolled patient for whom the CRF has not been collected
- Patient with the CRF collected: Enrolled patient for whom the CRF has been collected
- Finalized patient: Patient for whom the CRF has been collected and finalized at least once by data lock point
- Non-finalized patient: Patient for whom the CRF has been collected, but has not been finalized by data lock point
- Age: If the month and day of starting Leuplin PRO treatment is smaller than the month and day of birth, age will be calculated as year of starting Leuplin PRO treatment - year of birth - 1. If the month and day of starting Leuplin PRO treatment is equal to or greater than the month and day of birth, age will be calculated as year of starting Leuplin PRO treatment - year of birth. If the day of birth is unknown, 1 will be used for calculation.
- Time from diagnosis of prostate cancer to patient registration (months):
 - Actual number (units: month) = (“date of patient registration” - “date of diagnosis” + 1)/30.44
- BMI (kg/m^2): Calculated as body weight (kg)/height (m)² (displayed to one decimal place by rounding)

- Induration: AE with “induration” selected for “Specific symptom (multiple answers allowed)” in the column of [Adverse event: Injection site reaction] in the CRF
- Prostate cancer drug other than luteinizing hormone-releasing hormone (LH-RH) agonists or antagonists

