5.1.2 Occurrence of Adverse Drug Reactions/Infections

Patients included Safety population

in analysis:

Analysis item: ADRs, etc.

Analysis methods: For the aforementioned analysis item, analysis will be performed as described below.

- (1) Number of patients with an ADR, etc.
- (2) Number of ADR, etc.
- (3) Incidence of ADR, etc.
- (4) Type of ADR, etc.

For each analysis, events or patients will be counted as described below.

[Number of patients with an ADR, etc.]

- Number of patients who experienced an ADR, etc.

[Number of ADR, etc.]

- Number of reported ADR, etc. Multiple episodes of the same ADR, etc. in the same patient will be tabulated as the total number of episodes.

[Incidence of ADR, etc.]

- The incidence of ADR, etc. will be calculated as number of patients with an ADR, etc./number of patients included in safety evaluation $\times 100$.

[Type of ADR, etc.]

- ADRs, etc. will be coded using the MedDRA/J. ADRs, etc. will be classified by SOC and then tabulated by PT. For the SOC of investigations, ADRs, etc. will be sorted by HLGT (lined up in ascending order of HLGT code, but not output) and then tabulated by PT.
- For SOC, the number and incidence of ADR, etc. will be listed in internationally agreed SOC order. Multiple episodes of the same SOC in the same patient will be counted as 1 patient for the relevant SOC.
- For PT, the number and incidence of ADR, etc. will be listed in ascending order of PT code. Multiple episodes of the same PT in the same patient will be counted as 1 patient for the relevant PT.

5.1.3 Occurrence of Adverse Events Corresponding to Important Identified Risks, Important Potential Risks, or Important Missing Information

Patients included Safety population

in analysis:

Analysis item: AEs corresponding to important identified risks, important potential risks, or important missing information (described in Section 1.4 in Section 1, “Definitions of Terms, etc.”)

Analysis methods: For the aforementioned analysis item, analysis will be performed as described below.

- (1) Number of patients with an AE
- (2) Number of AE
- (3) Proportion of patients with an AE
- (4) Type of AE

For each analysis, events or patients will be counted as described below.

[Number of patients with an AE]

- Number of patients who experienced an AE

[Number of AE]

- Number of reported AE. Multiple episodes of the same AE in the same patient will be tabulated as the total number of episodes.

[Proportion of patients with an AE]

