5.3.3 Incidence of Induration Not Unrelated to Leuplin PRO by Factor

Patients included Safety population

in analysis:

Analysis item:	Induration not unrelated to Leuplin PRO
Stratification factors:	Age (years) [<65 years, $65-75$ years, ≥ 75 years] BMI (kg/m^2) [<18.5 , $18.5-25.0$, $25.0-30.0$, ≥ 30.0 , unknown]
	Full-treatment status of Leuplin PRO [Yes, no]
	Injection site [Extensor surface of the upper arm, deltoid region of the upper arm, abdomen, buttocks, other]
	Presence or absence of predisposition to hypersensitivity [No, yes, unknown]
	Presence or absence of concurrent allergic disease [No, yes]
	Disposition of allergic disease [Bronchial asthma, pollinosis, allergic rhinitis, allergic dermatitis]
	Presence or absence of treatment with LH-RH agonist or antagonist immediately before the start of Leuplin PRO treatment [No, yes]
	Disposition of treatment with LH-RH agonist or antagonist immediately before the start of Leuplin PRO treatment [Leuprorelin acetate 3.75 mg, leuprorelin acetate 11.25 mg, goserelin 3.6 mg, goserelin 10.8 mg, degarelix acetate]
Analysis methods:	For the aforementioned analysis item, analysis will be performed in each stratum of the stratification factor as described below. (1) Number of patients with induration not unrelated to Leuplin PRO and incidence of induration not unrelated to Leuplin PRO

5.4 Occurrence of Adverse Drug Reactions/Infections by Baseline Characteristics and Treatment Given

5.4.1 Occurrence of Adverse Drug Reactions/Infections by Baseline Characteristics and Treatment Given

Patients included Safety population
in analysis:

Analysis item: ADRs, etc.

Stratification factors:
Age (years) [<65 years, ≥ 65 years]
 <65 years, $65-75$ years, ≥ 75 years]
ECOG Performance Status [0, 1, 2, 3, 4]
Full-treatment status of Leuplin PRO [Yes, no]
Injection site [Extensor surface of the upper arm,
deltoid region of the upper arm,
abdomen, buttocks, other]

Disease status [Patient on postoperative adjuvant
therapy, patient with localized
cancer, patient with locally advanced
cancer, patient with metastatic
cancer]

Presence or absence of predisposition
to hypersensitivity [No, yes, unknown]

Presence or absence of concurrent
renal impairment [No, yes]

Presence or absence of concurrent
hepatic impairment [No, yes]

Presence or absence of concurrent
diabetes mellitus [No, yes]

Presence or absence of concurrent
hypertension [No, yes]

Presence or absence of concurrent
illness [No, yes]

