Presence or absence of history of
thromboembolism [No, yes, unknown]

BMI (kg/m^2) [<18.5 , $18.5-25.0$, $25.0-30.0$,
 ≥ 30.0 , unknown]

Presence or absence of treatment with [No, yes]

LH-RH agonist or antagonist
immediately before the start of Leuplin
PRO treatment
Presence or absence of treatment with [No, yes]
prostate cancer drug other than LH-RH
agonists or antagonists immediately
before the start of Leuplin PRO
treatment

Analysis
methods: For the aforementioned analysis item, analysis will be performed in each stratum
of the stratification factor as described below.

- (1) Number of patients with an ADR, etc. and incidence of ADR, etc.

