5.4.2 Occurrence of Adverse Drug Reactions/Infections by Age Group

Patients included Safety population
in analysis:
Analysis item: ADRs, etc.
Stratification factor: Age (years) [<65 years, >=65 years]
[<65 years, 65-<75 years, >=75 years]
Analysis methods: For the aforementioned analysis item, analysis as described in Section 5.1.2 will be performed in each stratum of the stratification factor.

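### The safety-factor tables give a count and crude incidence per stratum for 15 factors, with no contrast and no measure of uncertainty, so chance differences can easily look like safety factors

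*Protocol*

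**What the plan says.** Protocol 10.6.2 gives one method: "For ADRs reported during the observation period, the incidence will be tabulated by patient background factors", with disease status and renal and hepatic impairment among its examples, and also by treatment status. The wording is the same in every protocol version supplied. Protocol 10.1 leaves detailed methods to the SAP.

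SAP 5.4.1 lists 15 stratification factors, with age grouped in two ways. Its single analysis is "Number of patients with an ADR, etc. and incidence of ADR, etc". SAP 5.4.2 to 5.4.16 then take the factors one at a time and state that "analysis as described in Section 5.1.2 will be performed in each stratum of the stratification factor". SAP 5.1.2 consists of patient counts, event counts, a crude percentage and listings by organ class and preferred term.

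SAP 5.3.3 lists nine factors for induration, two of which subdivide another. Its analysis is "Number of patients with induration not unrelated to Leuplin PRO and incidence of induration not unrelated to Leuplin PRO".

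SAP 1.1 defines summary statistics as "Collective term for number of patients, mean, standard deviation, maximum, minimum, and quartiles", which includes no interval or standard error. Neither document contains a risk difference, ratio, test, confidence interval, adjusted model or statement on multiplicity.

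**The concern.** The protocol section asks a comparative question: does ADR risk within the Leuplin PRO cohort differ by patient background or by how the drug was given? The tables answer with separate percentages, printed to two decimals under SAP 1.3, and nothing that shows how far two of them could differ by chance. With about 300 patients, many strata are likely to be small. A reader comparing them by eye across 15 factors will tend to notice the largest gaps, which are often the noisiest. A chance gap can then be taken for a safety factor, and a real one can be shrugged off as noise.

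The point concerns contrasts between strata inside one cohort. It does not concern the comparison with Leuplin SR.

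**Working it through.** **1. The plan's own figure.** Protocol 3.2 states: "The sample size of 300 patients was determined to detect ADRs with an incidence of 1% or higher at a probability of 95% or higher". The chance of at least one case is 1 - 0.99^300 = 0.951. The minimum n is ln 0.05 / ln 0.99 = 298.07, so 299. The stated 300 reproduces. It covers seeing one case in the whole cohort and says nothing about comparing strata.

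**2. Number of contrasts in SAP 5.4.1**, each stratum against the largest of its factor, leaving out unknown levels:

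| Factor | Contrasts |
|---|---|
| Age (two groups, and three groups) | 1 + 2 = 3 |
| ECOG (5 levels) | 4 |
| Injection site (5) | 4 |
| Disease status (4) | 3 |
| BMI (4) | 3 |
| Ten two-level factors | 10 |
| **Total** | **27** |

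Hypersensitivity, thromboembolism history and BMI each have an unknown level, which makes 30. If no factor has any effect, the number of 95% intervals expected to exclude zero is about 27 × 0.05 = 1.35 to 30 × 0.05 = 1.5. This expectation does not need the factors to be independent. The same count for SAP 5.3.3, treating its categories as mutually exclusive, is 2 + 3 + 1 + 4 + 1 + 1 + 3 + 1 + 4 = 20, or 22 with the unknown levels.

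**3. How often chance alone gives a two-fold gap.** *Assumptions, none of them in the documents:* true ADR incidence, stratum shares, two-fold (ratio at least 2 or at most 0.5) as a striking gap, and 15 independent two-level factors with no effect. For each simulated survey of 300 patients, the number with an ADR is binomial(300, p). Those patients are then split at random over each factor.

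| Minority share | 10% incidence | 20% | 30% |
|---|---|---|---|
| All 50% | 61% | 8% | 0.4% |
| All 20% | 88% | 36% | 8% |
| Five each at 10%, 20%, 50% | 90% | 50% | 19% |
| Evenly spaced from 3% to 50% | 94% | 56% | 35% |

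Entries are the share of surveys with at least one two-fold gap. If every minority stratum held only 10% of patients, the figures would be 98%, 77% and 41%. For one factor split 30 against 270, the chance is 27% at 10% incidence and 10% at 20%. Split 150 against 150, it is 7% and 0.5%.

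**4. What an interval would show.** Take 6/30 (20%) against 27/270 (10%). The Wilson limits are 9.5% to 37.3% and 7.0% to 14.2%. The Newcombe limits for the difference are:

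- lower: 0.100 - √(0.105² + 0.042²) = -0.013
- upper: 0.100 + √(0.173² + 0.030²) = 0.276

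The apparent doubling is a difference of 10 points with a 95% CI of -1 to 28.

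**5. Power for a real doubling.** At two-sided 0.05, power for 20% against 10% is 41% with 30 against 270 patients and 68% with 150 against 150. An interval that covers zero is therefore weak evidence that a factor is harmless.

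**The case against.** The strongest reply is that this is a single-cohort surveillance and that descriptive tables are a legitimate choice. Protocol 10.6.2 speaks of factors that may matter and promises only tabulation. Protocol 2.0 sets no risk-factor objective. Counts are printed beside percentages, so a stratum of nine patients is visible as nine, and a reader can work out an interval. This stands as a limit on the point, but it does not answer it. Descriptive output can carry uncertainty without becoming confirmatory, and intervals set out in the SAP are better than intervals worked out later for the gaps that caught the eye.

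A reader might infer more than the documents support:

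- *That the plan will report false factors.* No test, threshold or declaration of factors is planned, so no formal type I error is inflated. Chance gaps can easily mislead, but it does not follow that they will.
- *That a spurious two-fold gap is close to certain.* That holds only with low incidence or small strata. With balanced strata at 20% incidence it is 8%. Empty small strata also count as two-fold gaps, and real factors overlap (any concurrent illness includes diabetes and hypertension), while the any-factor figures assume independence.
- *That 15 factors mean about 0.75 chance findings (15 × 0.05).* Several factors have more than two levels, so the number of contrasts is 27 to 30.
- *That a factor should be named only when its interval excludes zero.* With 41% power for a doubling in a small stratum, such a rule would make dismissal the default in a safety screen.

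**Conclusion.** The point holds as a reporting gap. SAP 5.4.1 and 5.3.3 supply counts and crude percentages, with neither a contrast nor a measure of uncertainty, for a question that is comparative. This much is read directly from the documents.

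The size is conditional. Under the assumptions in the working, at least one chance two-fold gap appears in roughly 60-95% of surveys at 10% incidence, 10-55% at 20% and 0-35% at 30%. The figure is higher if most minority strata are as small as 10%, and lower if ADRs are common and strata balanced. The documents do not say which of these applies.

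**What to change.** In SAP 5.4.1 and 5.3.3:

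1. For each stratum against the largest stratum of its factor, add the difference in incidence with a Newcombe 95% CI.
2. State that the denominator is the stratum size. SAP 5.1.2 divides by all patients in the safety evaluation ("The incidence of ADR, etc. will be calculated as number of patients with an ADR, etc./number of patients included in safety evaluation"), and the stratified tables refer back to it.
3. State that the contrasts are exploratory and unadjusted for multiplicity. Give their number (27 in 5.4.1 without the unknown levels, 30 with them, before any pooling) and the number of intervals expected to exclude zero by chance (about 1.4 to 1.5). Give the corresponding count for 5.3.3.
4. Add no rule that declares or dismisses a factor according to whether its interval excludes zero.

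Protocol 10.6.2 needs no edit, since 10.1 leaves methods to the SAP. A multivariable model for induration is optional and not needed to close the gap.

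The cost is extra columns in two tables and a few sentences, with no new data. The intervals will be wide in small strata, which is an honest picture of what those strata can show.

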11.0 Posting of Surveillance Information

Surveillance information will be posted on the following open website before starting the surveillance:

- Japan Pharmaceutical Information Center-Clinical Trials Information

14.0 Other Necessary Matters

14.1 Revision of the Protocol

During the surveillance, attention will be paid to comprehend the status of progression of the surveillance, presence or absence of ADRs that are unexpected based on the precautions/serious ADRs, presence or absence of increased incidence of certain ADRs, and appropriateness of surveillance items, and this protocol will be reviewed and revised if necessary. If partial change to dosage and administration or indications is approved during the surveillance, the necessity of revising the protocol will be discussed if necessary, and the protocol will be revised as needed.

14.2 Actions to be Taken for Problems and Questions

If any safety problem is detected, data will be carefully examined to discuss measures.

Appendix Observation schedule

| Surveillance item | Time point of surveillance | Observation period | |
|----------------------------------|--|---|---------------------------|
| | | After 24 weeks or at discontinuation of observation | At the start of treatment |
| Patient registration | At patient registration | ○ | |
| | Date of administration of Leuplin PRO | ○ | |
| | Patient identification number | ○ | |
| | Patient initials | ○ | |
| | Date of birth | ○ | |
| Patient baseline characteristics | Assessment based on the exclusion criteria | ○ | |
| | Time of diagnosis of prostate cancer | | ○ |
| | ECOG Performance Status | | ○ |
| | Disease status | | ○ |
| | Diagnostic category | | ○ |
| | Predisposition to hypersensitivity | | ○ |
| | Concurrent illness | | ○ |
| | History of thromboembolism | | ○ |
| | Height, body weight | | ○ |
| Treatment given | Treatment status of prostate cancer drug immediately before the start of Leuplin PRO treatment | | ○ |
| | Treatment status of Leuplin PRO | ← ○ → | |
| Adverse event | Treatment status of prostate cancer drug other than Leuplin PRO | ← ○ → | |
| | Injection site reaction | ← ○ → | |
| | Adverse event other than injection site reaction | ← ○ → | |

○ : Performed

← ○ →: Performed throughout the period

Special Drug Use Surveillance Protocol

Special Drug Use Surveillance of Leuplin PRO for

Injection Kit 22.5 mg for “Prostate Cancer”

Sponsor Takeda Pharmaceutical Company Limited

Protocol number Leuprorelin-5002

Version number 3rd version

Date of preparation 5 September 2016

Table of Contents

| | | |
|--------|--|----|
| 1.0 | Background of the Surveillance | 0 |
| 2.0 | Objectives..... | 0 |
| 3.0 | Planned Sample Size and Rationale | 0 |
| 3.1 | Planned Sample Size | 0 |
| 3.2 | Rationale..... | 0 |
| 4.0 | Surveillance Population..... | 0 |
| 5.0 | Dosage and Administration | 1 |
| 6.0 | Planned Number of Medical Institutions by Department..... | 1 |
| 7.0 | Methodology | 1 |
| 7.1 | Observation Period..... | 1 |
| 7.2 | Request to and Contract with the Study Site | 1 |
| 7.3 | Method of Patient Registration..... | 1 |
| 7.4 | Entry into the (Electronic) Case Report Form and Electronic Signature..... | 1 |
| 8.0 | Planned Surveillance Period..... | 2 |
| 9.0 | Surveillance Items..... | 2 |
| 9.1 | Patient Registration | 2 |
| 9.2 | Patient Baseline Characteristics | 2 |
| 9.3 | Treatment Given..... | 3 |
| 9.4 | Adverse Events (AEs) | 4 |
| 10.0 | Analysis Items and Methods | 7 |

1.0 Background of the Surveillance

Since the amount of leuprorelin acetate administered in a single dose of Leuplin PRO for Injection Kit 22.5 mg (hereinafter referred to as Leuplin PRO) is as high as twice that of Leuplin SR for Injection Kit 11.25 mg (hereinafter referred to as Leuplin SR), and the time profile of serum leuprorelin concentration after administration differs between the two formulations, a special drug use surveillance (hereinafter referred to as the surveillance) is planned to evaluate potential effects of the differences on the safety.

This surveillance will be conducted in compliance with the ministerial ordinance on Good Post-Marketing Study Practice (GPSP) and related regulatory requirements.

2.0 Objectives

To investigate the safety of Leuplin PRO in patients with prostate cancer in routine clinical settings in order to evaluate potential effects of differences between Leuplin PRO and Leuplin SR, including the higher amount administered in a single dose and differences in time profile of serum drug concentration after administration, on the safety

3.0 Planned Sample Size and Rationale

3.1 Planned Sample Size

300 patients

3.2 Rationale

To evaluate potential effects of differences between Leuplin PRO and Leuplin SR, that is, difference amounts of leuprorelin acetate administered in a single dose and different time profiles of serum drug concentration after administration, on the safety, it was decided to investigate the occurrence of injection site reaction and other adverse drug reactions (ADRs) with an incidence of 1% or higher, including the time of onset, incidence, and seriousness.

The sample size of 300 patients was determined to detect ADRs with an incidence of 1% or higher at a probability of 95% or higher.

